### **6.3.2. Exploratory biomarker endpoints (Cohort A only)**

Peripheral blood and additional tumor tissue biomarkers consisting of the levels of cells, deoxyribonucleic acid (DNA), ribonucleic acid (RNA), or proteins that may be related to anti-tumor immune response or disease progression.

Summary statistics for pre-treatment biomarkers will be presented by treatment arm for Cohort A. Summary statistics for on-treatment biomarkers will additionally include the ratio to baseline for continuous biomarkers, and a contingency table for non-continuous biomarkers, as appropriate.

### **6.4. Subset Analyses (Cohort A only)**

Subset analyses, if applicable, will be performed for OS, EFS, and CR per investigator assessment as noted below, based on the FAS for the subgroups defined below.

The following subgroups will be defined and used for analyses:

- Randomization stratification factor(s)
  - Presence of CIS per IRT (EFS per investigator, and OS)
    - Yes (Reference)
    - No
  - Geography
    - US (Reference)
    - Western Europe and Canada
    - ROW
- Presence of CIS per CRF (EFS per investigator and OS only)
  - Yes (Reference)
  - No
- Age
  - Age < 65 years (Reference)
  - Age  $\geq$  65 years
- Sex
  - Male (Reference)
  - Female

- Race
  - White (Reference)
  - Asian
  - Black or African American
  - Other
- Ethnicity
  - Hispanic or Latino or of Spanish origin
  - Not Hispanic or Latino or of Spanish origin (Reference)
- TICE Strain
  - TICE (Reference)
  - No TICE
- BCG strain at induction
  - TICE (Reference)
  - RIVM
  - TOKYO172
  - BCG-1
  - CHINA D2PB302
- T1 disease at baseline per CRF (EFS per investigator and OS only)
  - Yes
  - No (Reference)

Subset analyses for EFS and OS will use the censoring rules described in Sections 6.1.1.1, Section 6.2.2.1 and Section 6.2.2.2.

Treatment arms will be compared for each endpoint using a 2-sided unstratified log-rank test for each subgroup level and the unstratified HR and its corresponding 95% CI will be computed per subgroup level.

Subset analyses for difference in CR rates will be performed and the 2-sided 95% CI will be provided.

All the subset analyses will be unstratified and exploratory; no adjustment for multiplicity will be performed. In the case of a low number of participants within a category (<5% of the FAS) and low number of events within the category (< 10 events) the categories will be pooled or in cases where no meaningful pooling can be performed, the category may not be summarized.

To assess the heterogeneity of treatment effects for EFS and OS across the subgroup levels, a Cox's regression models will be fitted with EFS and OS as the dependent variable,

respectively, and subgroup, treatment, and the treatment-by-subgroup interaction as explanatory variables.

- Model: treatment + subgroup + treatment×subgroup-variable

A p-value for the interaction test (Wald's test) will be provided together with the HR and corresponding 95% CI for the interaction model parameter.

The HR for EFS and OS and corresponding 95% CIs for each subgroup will be presented in a forest plot.

The difference in CR rates and corresponding 95% CIs for each subgroup will be presented in a forest plot.

## 6.5. Baseline and Other Summaries and Analyses

### 6.5.1. Baseline summaries

The following analyses will be based on the FAS overall and separately by treatment arm in Cohort A. Baseline data for Cohorts B1 and B2 will be provided in listings only.

#### 6.5.1.1. Demographic and baseline characteristics

Demographic characteristics will be summarized by treatment arm and overall in Cohort A using the following information from the 'Demography' and 'ECOG Performance Status' eCRF pages.

- Demographic characteristics
  - Sex: Male, Female
  - Race: White, Black or African American, Asian, American Indian or Alaska Native, Native Hawaiian or Other Pacific Islander, Multiracial, Not Reported
  - Ethnic origin:
    - Hispanic or Latino or of Spanish origin
    - Not Hispanic or Latino or of Spanish origin
    - Not Reported
  - Age (years): summary statistics
  - Age categories:
    - < 65 years, ≥ 65 years
    - 65-<75, 75-<85, ≥ 85 years
  - Geographic Region (as applicable):
    - North America
    - Latin America
    - Western Europe
    - Eastern Europe

- Middle East
- Australasia
- Asia
- Africa
- Eastern Cooperative Oncology Group (ECOG) Performance Status at baseline: 0, 1, 2, 3, and 4

Center codes will be used for the determination of the participant's geographic region.

The listing of demographics and baseline characteristics will include the following information: participant identifier, treatment arm/cohort, age, sex, race, ethnicity, and ECOG performance status at baseline.

#### **6.5.1.2. Medical history**

Medical history will be coded using the most current available version of Medical Dictionary for Regulatory Activities (MedDRA) and will be summarized from the 'Significant Medical History' eCRF page. Medical history will be summarized as the numbers and percentages of participants by MedDRA PT as event category and MedDRA primary SOC as summary category. Each participant will be counted only once within each PT or SOC.

Medical history will be displayed in terms of frequency tables: ordered by primary SOC and PT in alphabetical order.

#### **6.5.1.3. Disease characteristics**

Information on disease characteristics collected on 'Primary Diagnosis', 'Primary Cancer Therapy', 'Substance Use', and disease assessment eCRF pages will be summarized overall and by treatment arm in Cohort A and listed for Cohort B1 and B2. Summary statistics for Cohort A and a listing only for Cohorts B1 and B2 will be presented for the following, as applicable.

From the 'Primary Diagnosis' and 'Primary Cancer Therapy' eCRF page:

- Primary diagnosis (summarize all categories (Urothelial (transitional cell) carcinoma, urothelial (transitional cell) carcinoma with squamous differentiation, urothelial (transitional cell) carcinoma with glandular differentiation, urothelial (transitional cell) carcinoma with variant histology (specify), Other) collected in the 'Primary Diagnosis' eCRF page)
- Disease Recurrence Type (Recurrence, Newly Diagnosed) (Cohort A only)
- Time since initial diagnosis to 'start date' (months), defined as ('start date' – date of initial diagnosis)/30.4375
- Reason participant did not undergo cystectomy (Participant Refused, Participant Ineligible) (Cohorts B1 and B2 only)

Separately from the disease status eCRF pages based on investigator assessment ('Cystoscopy', and 'Oncology Biopsy') at baseline, except for Cohort B1 where the BICR biopsy data at baseline will be used:

- CIS per CRF: Yes, No
- Number of tumors identified by cystoscopy: Single, Multiple, Unknown
- Size of largest tumor identified by cystoscopy: <3cm, ≥3cm, Unknown
- Highest grade of tumors identified by biopsy: High, Low
- Worst T stage: CIS, Ta, T1, T2, T3, T4

From the 'Substance Use' eCRF page:

- Smoking history (never smoker vs current vs former smoker)

Listing of disease history will be provided for Cohort A and Cohorts B1 and B2 with all relevant data (as collected on the 'Primary Diagnosis' and 'Primary Cancer Therapy' eCRF pages) and derived variables as above.

#### **6.5.1.4. Prior anti-cancer therapies**

The prior anti-cancer therapies are collected under the 'Prior Cancer Therapy' and 'Prior anti-cancer Surgery' eCRF pages.

The number and percentage of participants in each of the following anti-cancer therapy categories will be tabulated:

- Participants with at least one type of prior anti-cancer therapy
- Participants with at least one prior anti-cancer drug therapy
- Participants with at least one prior anti-cancer surgery

Prior anti-cancer drug therapy will be summarized as follows based on the number and percentage of participants with the following:

- At least one prior anti-cancer drug therapy
- Number of prior anti-cancer drug therapy regimens: missing, 1, 2, 3, ≥4

The following will be provided in a listing:

- Prior BCG strain (Cohorts B1 and B2)
- Number of prior BCG doses (Cohorts B1 and B2)
- Prior BCG failure: persistence of CIS, recurrence (Cohorts B1 and B2)

The prior anti-cancer drugs will also be summarized based on the number and percentage of participants by the drug class and preferred term. A participant will be counted only once within a given drug class and within a given drug name, even if he/she received the same medication at different times. The summary will be sorted on decreasing frequency of drug

class and decreasing frequency of drug name in a given drug class. In case of equal frequency regarding drug class (respectively drug name), alphabetical order will be used.

Prior anti-cancer drug therapies will be included in the listing that follows with a flag to identify prior drug therapies. These will include the participant identification number, and all the relevant collected data-fields on the “Prior Cancer Therapy” eCRF page.

- Listing of anti-cancer drug therapies

### **6.5.2. Study conduct and participant disposition**

The following analyses will be performed based on the FAS overall (screening only) and separately by treatment arm in Cohort A. Data for Cohorts B1 and B2 will be provided in listings only.

#### **6.5.2.1. Participant disposition**

The percentages below will be calculated based on the number of participants screened. The following will be summarized:

- Total number of participants screened overall
- n (%) of participants who discontinued prior to ‘start date’ overall and by reasons for discontinuation.

The percentages below will be calculated based on the number of participants in the FAS. Discontinuations will be presented overall and by reason for discontinuation:

- n (%) in each of the analysis sets defined in [Section 4](#)
- n (%) discontinued prior to receiving any study drug
- PF-06801591 disposition
  - n (%) discontinued treatment with PF-06801591 and by reason
  - n (%) ongoing treatment with PF-06801591
  - n (%) completed treatment with PF-06801591
- BCG disposition, separately for induction, re-induction and maintenance periods:
  - n (%) entering each period
  - n (%) discontinued treatment with BCG and by reason
  - n (%) ongoing treatment with BCG
  - n (%) completed treatment with BCG
- Follow-up
  - n (%) entered follow-up
  - n (%) discontinued follow-up and by reason
  - n (%) ongoing

A listing of participant disposition will be provided.

A listing of participant discontinuations related to COVID-19 will be presented.

For Cohort A, the results of the randomization algorithm (according to IRT) will be summarized as follows:

- Number and percentage of randomized participants overall, by region, by country, and by center
- Number and percentage of randomized participants by randomization strata (IRT)
- Cross tabulation: stratum by IRT vs. stratum by eCRF where CIS is derived based on the data entered by the investigator on the “Oncology Biopsy” eCRF at Screening.

#### **6.5.2.2. Protocol deviations**

All protocol violations that impact the safety of the participants and/or the conduct of a study and/or its evaluation will be reported. These include:

- Participants who are dosed on the study despite not satisfying the inclusion criteria
- Participants who develop withdrawal criteria whilst on the study but are not withdrawn
- Participants who receive the wrong treatment
- Participants who receive an excluded concomitant medication
- Deviations from Good Clinical Practice (GCP).

A listing of protocol deviations will be provided.

A listing of protocol deviations related to COVID-19 will be provided. The identification of these and other CSR-reportable deviations will be based on the inclusion/exclusion criteria or other criteria presented in the protocol.

A listing of participants impacted by COVID-19 will be provided to describe how the individual's participation was altered in terms of investigator disease assessments, including a row for every follow-up visit, as well as extra rows for missed follow-up visits.

#### **6.5.3. Study treatment compliance and exposure**

The following analyses will be based on the safety analysis set by treatment arm in Cohort A for the following study drugs (administered alone or in combination):

- **BCG** suggested administration (full dose per BCG labeling guidelines):
  - Induction period: One dose every week for 6 consecutive weeks (i.e., C1D1, C1D8, C1D15, C1D22, C2D1, and C2D8).
  - Re-induction period, up to 6 consecutive weeks (following induction period, for participants with CIS at randomization who have persistent disease and participants with recurrence of high-grade Ta disease); suggested schedule is C4D1, C4D8, C4D15, C4D22, C5D1, and C5D8. Maintenance will then begin on C7D1. If TURBT

is performed, schedule for BCG re-induction should be modified according to the product label.

- **Maintenance period (Arm A and Arm C):** D1, D8, D15 during Cycles C4, C7, C13, C19 and C25. For participants that have a re-induction period, the maintenance period will begin at C7D1.
- **PF-06801591** administration: SC Q4W (last dose at Cycle 25) at a dose of 300 mg for Cohorts A and B1 or SC Q6W (last dose at Cycle 17) at 600 mg for Cohort B2. Doses of PF-06801591 may be recorded in the eCRF as 300 mg, 600 mg (Cohort B2 only), 0 mg, or ‘partial dose’, where a ‘partial dose’ is captured as “UNK” on the PF-06801591 CRF dosing page. A ‘partial dose’ should not be considered a 0 mg dose and must be included in the derivations for first and last dose of study drug.

#### **6.5.3.1. Exposure to study drug**

Exposure to each study drug will be summarized for Cohort A as follows.

##### **Duration of exposure to BCG (weeks) =**

- Overall: (last dose date of BCG – first dose date of BCG +7)/7.

##### **Duration of exposure to PF-06801591 (weeks) =**

For Cohorts A:

(last dose date of PF-06801591 – first dose date of PF-06801591 +28)/7

The number and percentage of participants with 1, 2, 3, 4, 5, 6 or > 6 non-zero doses of BCG during induction, 1, 2, 3, 4, 5, 6 or > 6 non-zero doses of BCG during re-induction, and 1 through 15 and >15 non-zero doses of BCG during maintenance will be summarized. In addition, the median and range of number of non-zero doses of BCG received by a participant in each period will be provided.

The number and percentage of participants with each of 1 through 25 or > 25 (Cohorts A) non-zero doses of PF-06801591 will be summarized. In addition, the median and range of non-zero doses of PF-06801591 received by a participant will be provided.

The summary of exposure to study drug will include:

- Duration of exposure to PF-06801591 (overall)
- Duration of exposure to BCG (overall)
- Doses received for PF-06801591 (overall)
- Doses received for BCG (overall and by period)

A listing of exposure to BCG and PF-06801591 will be provided with relevant information for Cohort A and Cohorts B1 and B2, as applicable.

### **6.5.3.2. Dose reductions**

Applicable to BCG. Dose reduction is defined as actual non-zero dose < 90% of the planned dose.

The number and percentage of participants with at least one dose reduction as well as a breakdown of the number of dose reductions (1, 2, 3, 4, 5,  $\geq 6$ ) will be summarized.

Applicable to PF-06801591. The dose for PF-06801591 can be entered as 0, 300 mg, 600 mg (Cohort B2 only), or ‘partial dose’. Where a ‘partial dose’ is captured as “UNK” on the PF-06801591 CRF dosing page for all cohorts. For Cohort B2, 300mg dose is also a ‘partial dose’. The number and percentage of participants with at least one ‘partial dose’ dose as well as a breakdown of the number of partial doses (1, 2, 3, 4, 5,  $\geq 6$ ) will be summarized for Cohort A.

### **6.5.3.3. BCG retention interruption**

An interruption in BCG retention based on void time will be assessed. A void time  $\leq$  30 minutes,  $>30$  minutes and  $\leq 1$  hour, and  $>1$  hour and  $< 2$  hours will be summarized by number and percentage of participants. In addition, the number and percentage of participants with at least one retention interruption as well as a breakdown of the number of retention interruptions (1, 2, 3,  $\geq 4$ ) by time category and overall will be summarized.

### **6.5.3.4. Dose delays**

Applicable to PF-06801591 and BCG for Cohort A.

Dose Delay is the difference between the actual time between two consecutive non-zero doses and the planned time between the same two consecutive non-zero doses. ‘Unknown’ dose amounts for PF-06801591 are considered a non-zero dose.

#### **For PF-06801591:**

For Cohort A: Dose Delay for Dose x (days) = Date of Dose x – Date of Dose (x-1) – 28

#### **For BCG:**

Dosing in each period will be determined by the CRF disposition pages for when each period started and ended based on when participants started the next period.

- Induction: Dose Delay for Dose x (days) = Date of Dose x – Date of Dose (x-1) – 7,
- Re-induction: Dose Delay for Dose x (days) = Date of Dose x – Date of Dose (x-1) – 7,
- Maintenance:

Dose Delay for Dose x (days) = Date of Dose x – Date of Dose (x-1) – 7, for doses within a cycle (i.e. between Days 1, 8, and 15 of Cycle 4, Cycle 7, Cycle 13, Cycle 19 and Cycle 25).

Dose Delay for Dose x (days) = Date of Dose x – Date of Dose (x-1) – 70, between the last dose of the cycle prior to Cycle 7 and next dose (i.e. between Cycle 4 Day 15 to

### Cycle 7 Day 1)

Dose Delay for Dose x (days) = Date of Dose x – Date of Dose (x-1) – 154, between the last dose of the previous cycle (Cycle 7 and after) and next dose (i.e. between maintenance cycles 7 to 25 from Day 15 to Day 1 (i.e. Cycle 7 Day 15 to Cycle 13 Day 1)

For Cohort A, dose delays will be grouped into the following categories, Cycles 1-3 and Cycle 4-25, for both BCG and PF-06801591.

#### Cycles 1-3 (Cohort A only)

- No delay (0-3 days window)
- 4 or more days delay

#### Cycles 4-25 (Cohort A)

- No delay (0-7 days window)
- 8 or more days delay

For example, for PF-06801591, administered on a 4-week schedule, if a participant receives PF-06801591 on Cycle 1 Day 1 (study day 1) and the next PF-06801591 administration is on study day 33, this is considered as a 4-day delay.

The number and percentage of participants with delayed study drug administration and maximum length of delay, i.e., the worst case of delay if participants have multiple dose delays will be summarized.

#### **6.5.4. Concomitant medications and non-drug treatments**

The following analyses will be based on the safety analysis set by treatment arm in Cohort A.

**Concomitant medications** are medications, other than study drugs, which started prior to first dose date of study treatment and continued during the on-treatment period as well as those started during the on-treatment period. Concomitant medications will be summarized from the 'Concomitant Medications' eCRF page.

Summary of concomitant medications will include the number and percentage of participants by Anatomical Therapeutic Chemical (ATC) Classification level 2 and preferred term. A participant will be counted only once within a given drug class and within a given drug name, even if he/she received the same medication at different times. If any concomitant medication is classified into multiple ATC classes, the medication will be summarized separately under each of these ATC classes. The summary tables will be sorted on decreasing frequency of drug class and decreasing frequency of drug name in a given drug class. In case of equal frequency regarding drug class (respectively drug name), alphabetical order will be used. In case any specific medication does not have ATC classification level 2 coded term, it will be summarized under 'Unavailable ATC classification' category.

A listing of concomitant medications will be created with the relevant information collected on the 'Concomitant Medications' eCRF page.

#### 6.5.5. Subsequent anti-cancer therapies

The following analyses will be based on the FAS by treatment arm in Cohort A. Anti-cancer drug treatment will be provided in a data listing with data retrieved from 'Follow-up Cancer Therapy' eCRF page. Number and percentage of participants with any anti-cancer therapy will be tabulated overall and by type of therapy based on the data collected from the 'Follow-up Cancer Therapy', 'Follow-up Radiation Treatment' and 'On Study & Follow-up Cancer Surgery' eCRF pages for Cohort A only.

A listing of anti-cancer therapies will be provided for Cohort A and Cohorts B1 and B2.

#### 6.6. Safety Summaries and Analyses

The Safety Analysis Set will be the primary analysis set for safety evaluations. Summaries of AEs and other safety parameters will be based on the safety analysis set by treatment arm in Cohort A and by Cohorts B1 and B2.

##### 6.6.1. Adverse events

TEAEs are those events with onset dates occurring during the on-treatment period as defined in [Section 3.5.1](#).

All analyses described will be based on TEAEs (started during the on-treatment period) if not otherwise specified. The AE listings will include all AEs (whether treatment-emergent or not). AEs outside the on-treatment period will be flagged in the listings.

- **Related Adverse Events:** adverse events with relationship to study treatment (as recorded on the AE eCRF page, Relationship with study treatment = Related) reported by the investigator and those of unknown relationship (i.e., no answer to the question 'Relationship with study treatment'). Related AEs are those related to any study drug (i.e., at least one of the study drugs).
- **Serious Adverse Events (SAE):** serious adverse events (as recorded on the AE eCRF page, Serious = Yes).
- **Adverse Events Leading to Interruption of Study Treatment:** adverse events leading to interruption of study treatment (as recorded on the AE eCRF page, Action taken with study treatment = Drug interrupted).
- **Adverse Events Leading to Discontinuation of Study Drug:** adverse events leading to discontinuation of study drug (as recorded on the AE eCRF page, Action taken with study treatment = Drug withdrawn).
- **Adverse Events Leading to Death:** adverse event leading to death (as recorded on the AE eCRF page, Outcome = Fatal, as well as AEs of Grade 5).

- **Immune-related Adverse Events (irAE):** irAEs (as identified according to the methodology outlined in Appendix 1 for a pre-specified search list of MedDRA PTs documented in the Safety Review Plan [SRP] and finalized for analysis of this study's data prior to database lock)
- **Injection site reaction (ISR) related to PF-06801591:** adverse events with relationship to PF-06801591 (as recorded on the AE eCRF page, Relationship with study treatment = Related) reported by the investigator and those of unknown relationship (i.e., no answer to the question 'Relationship with study treatment'), and with high level term (HLT) of Injection site reactions.

Unless otherwise specified, AEs will be summarized by number and percentage of participants with the AE in the category of interest as described above, by treatment arm in Cohort A and by Cohorts B1 and B2, primary SOC, and PT in decreasing frequency based on the frequencies observed for Arm A (for Cohort A) and Cohort B1 (for Cohorts B1 and B2).

Each participant will be counted only once within each SOC or PT. If a participant experiences more than one AE within a SOC or PT for the same summary period, only the AE with the strongest relationship or the worst severity, as appropriate, will be included in the summaries of relationship and severity.

#### 6.6.1.1. All adverse events

Adverse events will be summarized by worst severity (according to CTCAE v5.0) per participant, using the latest version of MedDRA PT as event category and MedDRA primary SOC body term as Body System category.

In case a participant has AEs with missing and non-missing grades, the maximum of the non-missing grades will be displayed. No imputation of missing grades will be performed.

The following tables will be created:

- The overall summary of AEs table will include the frequency (number and percentage) of participants with each of the following by treatment arm in Cohort A and by Cohorts B1 and B2, as applicable:
  - TEAEs
  - TEAEs, Grade  $\geq 3$
  - Related TEAEs
  - Related TEAEs, Grade  $\geq 3$
  - TEAEs leading to interruption of PF-06801591
  - TEAEs leading to interruption of BCG
  - TEAEs leading to discontinuation of PF-06801591
  - TEAEs leading to discontinuation of BCG
  - TEAEs leading to discontinuation of all study drugs

- Related TEAEs leading to discontinuation of PF-06801591
- Related TEAEs leading to discontinuation of BCG
- Related TEAEs leading to discontinuation of all study drugs
- Serious TEAEs
- Related Serious TEAEs
- TEAEs leading to death
- Related TEAEs leading to death
- irAEs
- ISRs related to PF-06801591

- TEAEs by SOC and PT and worst grade
- Related TEAEs by SOC and PT and worst grade
- TEAEs leading to death by SOC and PT (Cohort A only)
- Related TEAEs leading to death by SOC and PT (Cohort A only)
- COVID-19 TEAEs by SOC and PT, as noted on the ‘Adverse Event’ eCRF.

A listing of all AEs will be provided with relevant information (e.g., SOC/PT, start and stop dates, causality, study drug action, medication error, SAE, and concomitant medications).

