7. DISCONTINUATION OF STUDY INTERVENTION AND PARTICIPANT DISCONTINUATION/WITHDRAWAL

7.1. Discontinuation of Study Intervention

For participants in Cohort A, it may be necessary for a participant to permanently discontinue one of the two study interventions. In that case, please note that the participant will still continue with the other study intervention. If it is necessary for the participant to permanently discontinue both PF-06801591 and BCG, the participant will remain in the study and move into the post-treatment follow-up period to allow for an adequate evaluation of the study objectives based on the prespecified estimands.

Note that permanent discontinuation of study treatment does not represent withdrawal from the study.

Participants may withdraw from study treatment at any time at their own request, or they may be withdrawn at the discretion of the investigator or sponsor for safety or behavioral reasons, or the inability of the participant to comply with the protocol-required schedule of study visits or procedures at a given study site.

Reasons for withdrawal of study treatment in Cohorts A, B1, and B2 may include:

- Completion of study treatment (25 cycles for Cohort A, Arms A, B and C, and Cohort B1, and 17 cycles for Cohort B2)
- Participants with CIS at baseline who do not achieve a CR within 6 months of initiating study intervention will be withdrawn from study treatment
- Recurrence of high-grade disease (Section 10.9) or progression of disease
- Global deterioration of health status requiring discontinuation of study treatment
- Unacceptable toxicity
- Pregnancy
- Significant protocol violation
- Lost to follow-up
- Participant refused further treatment
- Study terminated by sponsor
- Death

Discontinuation of study treatment for abnormal liver function should be considered by the investigator when a participant meets one of the conditions outlined or if the investigator believes that it is in best interest of the participant. See Section 10.6 for details.

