### BCG Naïve Cohort (Cohort A)

- Arm A: PF-06801591 + BCG (IND and MNT)
- Arm B: PF-06801591 + BCG (IND only)
- Arm C: BCG only (IND and MNT)

where IND=induction and MNT=maintenance

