#### **6.6.1.2. Adverse events leading to discontinuation of study drug**

The frequency (number and percentage) of participants with each of the following will be presented for TEAEs leading to discontinuation of each study drug, by treatment arm in Cohort A and by Cohorts B1 and B2, as applicable:

- TEAEs leading to discontinuation of PF-06801591 by SOC and PT
- Related TEAEs leading to discontinuation of PF-06801591 by SOC and PT
- TEAEs leading to discontinuation of BCG by SOC and PT (Cohort A only)
- Related TEAEs leading to discontinuation of BCG by SOC and PT (Cohort A only)
- TEAEs leading to discontinuation of all study drugs by SOC and PT (Cohort A only)
- Related TEAEs leading to discontinuation of all study drugs by SOC and PT (Cohort A only)

The listing of all AEs leading to discontinuation of study drug will also be provided with the relevant information.

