##### **6.6.4.1. Immune related adverse events**

The criteria for classification of an adverse event as an irAE is described in Appendix 1. The frequency (number and percentage) of participants with each of the following will be presented for irAEs, by treatment arm in Cohort A and by Cohorts B1 and B2, if applicable:

- irAEs leading to death, by Cluster and PT (Cohort A only)
- irAEs, by Cluster, PT, and worst Grade
- irAEs, Any Grade and Grade  $\geq 3$ , by Cluster and PT (Cohort A only)
- irAEs leading to discontinuation of PF-06801591, by Cluster and PT
- irAEs leading to discontinuation of BCG, by Cluster and PT (Cohort A only)
- irAEs leading to discontinuation of all study drugs, by Cluster and PT (Cohort A only)
- Serious irAEs, by Cluster and PT

The listing of all irAEs will also be provided with the relevant information with a flag for irAEs with onset outside of the on-treatment period for irAE (i.e., irAEs not meeting the programmatic criteria in Step 2 as outlined in Table 25 of Appendix 1)

The frequency (number and percentage) of participants with potential irAEs (i.e., AEs meeting the programmatic criteria Step 1 and Step 2 outlined in Table 25 of Appendix 1) will also be presented by treatment arm in Cohort A and by Cohorts B1 and B2.

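### The SAP plans no any-drug row for adverse events leading to discontinuation, and its only cross-drug row, all study drugs, is not comparable between the three arms

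*SAP*

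**What the plan says.** The overall adverse event table in SAP 6.6.1.1 has three discontinuation rows by arm: "TEAEs leading to discontinuation of PF-06801591", "TEAEs leading to discontinuation of BCG" and "TEAEs leading to discontinuation of all study drugs". Each also has a treatment-related version. SAP 6.6.1.2 repeats the three by system organ class and preferred term and adds a listing. SAP 6.6.4.1 repeats them for immune-related events. None of these sections has a row for discontinuation of any study drug.

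SAP 6.6.1 defines the underlying category as "adverse events leading to discontinuation of study drug (as recorded on the AE eCRF page, Action taken with study treatment = Drug withdrawn"). It does not say whether all study drugs means one event that withdraws both drugs or separate events over time. Nor does it say how a drug already completed is treated.

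The arms differ in what there is to stop. Arm A has sasanlimab plus BCG induction and maintenance, Arm B has sasanlimab plus BCG induction only, and Arm C has BCG alone (SAP 3.4.1). When one drug is stopped for good, Protocol 7.1 says that "the participant will still continue with the other study intervention".

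**The concern.** The regimen's overall safety profile is a stated secondary objective (SAP Table 2). A natural question is how often toxicity ended part or all of treatment in each arm. The sasanlimab row is empty by design in Arm C. The BCG row sets 6 planned induction doses in Arm B against 21 in Arms A and C. That leaves all study drugs as the only row that spans the drugs, and a reader of the summary table is likely to compare it across arms. It asks for a different number of withdrawals in each arm, in a direction that favours the sasanlimab arms.

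**Working it through.** The plan states no rate or target for these rows, so there is no figure to reproduce. The check is of the schedule and the counting.

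**Schedule** (Protocol 4.1.1, SAP 6.5.3), with day = 28 × (cycle − 1) + day in cycle:
- Last induction BCG dose, C2D8: 28 + 8 = day 36.
- Last suggested re-induction dose, C5D8: 112 + 8 = day 120.
- Last sasanlimab dose, C25D1: 672 + 1 = day 673.
- Planned BCG doses in Arms A and C without re-induction: 6 + 5 × 3 = 21.
- Share of the C1D1–C25D1 span after day 36: (673 − 36)/672 = 94.8%, holding 23 of 25 sasanlimab doses. After day 120: (673 − 120)/672 = 82.3%, holding 20 of 25.

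**Arm A against Arm C.** Let S and B be the proportions stopping sasanlimab and BCG for an adverse event.
- Arm C: all = any = B.
- Arm A: all lies between max(0, S + B − 1) and min(S, B); any = S + B − both.

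Since min(S, B) ≤ B, Arm A cannot exceed Arm C on the all-drugs row unless its BCG-stop rate is itself higher. This needs no assumption about S.

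For scale, assume S and B each between 5% and 20%, B equal in the two arms, and independent stops:

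| B | S | Arm C, all = any | Arm A, all | Arm A, any |
|---|---|---|---|---|
| 5% | 5% | 5% | 0.25% | 9.75% |
| 15% | 20% | 15% | 3.0% | 32.0% |
| 20% | 20% | 20% | 4.0% | 36.0% |

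With 1056/3 = 352 per arm, the middle line is about 11 participants in Arm A against 53 in Arm C on the all-drugs row, and about 113 against 53 on an any-drug row. With maximum overlap instead of independence, Arm A would read 15% on all and 20% on any.

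**Arm B.** If both drugs must be marked withdrawn, the all-drugs row is capped by Arm B's own BCG-withdrawal rate. Take 15% over the full BCG course as above, no re-induction and S = 20%. Spreading the risk evenly over time gives a cap of 1 − 0.85^(36/673) = 0.9%; spreading it by planned dose gives 1 − 0.85^(6/21) = 4.5%. If completed BCG counts as satisfied, the cap is S = 20%. The SAP does not choose between these readings.

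**Recovering the any-drug rate from the planned rows.** If all is counted per participant over time as both drugs withdrawn, any = S + B − all; here 20% + 15% − 3% = 32%. If all needs a single event that stops both, any is only bounded, between max(S, B) and S + B − all; for the same row values, 20% to 32%.

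**The case against.** A reader might infer that the table hides excess intolerance in the sasanlimab arms. The documents do not support that. The sasanlimab and BCG rows stand in the same table by arm, SAP 6.6.1.2 adds detail and a listing, and SAP 6.5.2.1 gives disposition for each drug by reason, with BCG split by period. A 20% sasanlimab discontinuation rate would be printed directly above the all-drugs row.

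A reader might also take the all-drugs row as the plan's between-arm measure of tolerability. No section gives it that role, and Protocol 9.4.2 plans simple descriptive safety summaries.

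A third inference is that the row cannot be met in Arm B after week 6. That goes too far. BCG withdrawn for an event in induction followed by later withdrawal of sasanlimab would count if events are combined per participant. A rule for completed BCG could make it count. Re-induction may also apply: Protocol 4.1.1 and 6.1.2 and SAP 6.5.3 restrict only maintenance to Arms A and C, while the BCG row holding re-induction in the maintenance-period Schedule of Activities (Protocol 1.3) is labelled Arms A and C.

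Finally, an any-drug row is not neutral. At equal BCG-stop rates Arm A can never read below Arm C on it, and stopping one drug while continuing the other is not the end of treatment. This stands, and it is why the new row should accompany the existing one.

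What the objections leave in place is the unequal counting, the undefined derivation and the absence of a comparable figure.

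**Conclusion.** The point holds as a gap in comparability. The Arm A against Arm C limit follows from the definitions, given equal BCG-stop rates. The percentages are illustrations at assumed rates, not predictions. For Arm B the supportable statement is that the handling of completed BCG is undefined; on a literal reading of drug withdrawn, a sasanlimab withdrawal after BCG completion is not counted, and most of the sasanlimab schedule falls there (94.8% of the span, or 82.3% where re-induction is given). The components are reported, so no information is lost if the all-drugs row turns out to be a per-participant count over time. If it is not, the any-drug rate can only be bounded. This is an inexpensive improvement to the safety tables; no efficacy conclusion depends on it.

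**What to change.** - In SAP 6.6.1.1, 6.6.1.2 and 6.6.4.1, add rows by arm for adverse events, related adverse events and immune-related events leading to discontinuation of any study drug. Show them alongside the all-drugs rows, not in place of them.
- In SAP 6.6.1, state that all study drugs is counted per participant across events, and that in Arm B a withdrawal of sasanlimab for an adverse event after BCG is completed counts as ending all remaining study treatment. With that rule the subtraction S + B − all no longer gives the any-drug rate in Arm B, so the any-drug row has to be printed.
- Reconcile Protocol 4.1.1 and 6.1.2 and SAP 6.5.3 with the Schedule of Activities on whether Arm B may receive BCG re-induction. The Protocol 6.1 intervention table also lists maintenance BCG in the Arm B dosage cell although the arm is named induction only; that must be reconciled too.

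The any-drug rows use the action-taken field already collected. The Arm B rule also needs a link to BCG disposition data. The remaining cost is a few table rows and a discontinuation figure that will look less favourable in Arms A and B.
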